1. INTRODUCTION

1.1. Background (Amended 16 October 2017)

Dengue, the most common arthropod-borne viral disease worldwide, is caused by four types of dengue viruses (DENV 1-4), transmitted primarily by *Aedes aegypti*, a mosquito that is highly adapted to urban environments. Dengue infection can cause a range of clinical illnesses, from inapparent to a life threatening hemorrhagic disease, often associated with pre-existing heterotypic dengue virus antibodies.

An estimated 2.5 billion people are at risk of infection in tropical and subtropical countries worldwide (WHO, 2009) where major urban epidemics are responsible for substantial social and economic burden. Dengue has drastically increased in the last two decades in Central and South America with Brazil being one of the most affected countries (Siqueira-Junior, 2008). In Central Brazil, an almost 20-fold increase in reported cases of dengue have been reported from 1990 (1,660 cases) to 2000 (20,552 cases) (Siqueira, 2004). In all of Brazil, the number of yearly reported cases increased from 124,827 in 1995 to more than 1 million in 2010 (PAHO, 2011)

Currently, strategies to reduce disease burden rely mainly on mosquito control and human preventive behaviour modification, as treatment is limited to supportive care. The World Health Organization (WHO) has, therefore, considered the development of a vaccine a priority research area (Brandt, 1990), and a number of vaccine candidates are under development or being tested in clinical trials (Thomas, 2011).

In preparation for phase III trials, the WHO recommends that the primary efficacy endpoint be the presence of DENV in a patient with signs and/or symptoms of dengue disease (WHO, 2009; Edelman, 2008). However, mild cases of dengue are largely underreported, as shown in dengue cohort studies and capture-recapture studies (Wichmann, 2011; Vong, 2011; Suaya, 2007). For example, in Nicaragua an active dengue surveillance system in children was able to detect approximately 14 to 28 (average 21.3) times more dengue cases each year per 100,000 persons than passive surveillance among similar paediatric populations (Standish, 2010).

Zika is a flavivirus and chikungunya virus is a member of the alphavirus genus, and Togaviridae family. These are emerging mosquito-borne viral diseases in Latin America. Zika virus infections have been laboratory confirmed in 19 states in Brazil between April and December 2016 [Boletim Epidemiológico, 2017]. In 2016, until epidemiological week 52, 215,319 cases were reported and 130,701 were confirmed [Boletim Epidemiológico, 2017].

In 2015, 20,661 autochthonous suspected chikungunya cases were reported in Brazil [Boletim Epidemiológico, 2017]. In 2016, 271,824 reported cases and 151,318 were confirmed up to epidemiological week 47 [Boletim Epidemiológico, 2017]. Zika and chikungunya viruses cause symptoms often similar to dengue during the acute phase of illness.

Another challenge when conducting vaccine trials is to select geographic settings where the incidence of dengue would allow for a reliable assessment of vaccine efficacy. ***Endemicity for more than one dengue virus type is also*** highly desirable. Thus, selection of geographically diverse sites can potentially maximize the likelihood of having a sufficient number of exposed individuals for the conduct of a vaccine trial. Finally, ***identifying*** all other coexisting flaviviruses circulating at potential study sites ***is important***, as infection by such viruses might, in theory, modulate immune response and clinical course of dengue infection.

In this study, we will estimate the incidence of dengue infection and disease in a cohort of subjects recruited from different geographic areas over time in Brazil. The study will also identify and train potential sites for the conduct of phase III studies in the future.

1.2. Rationale for the study

The estimation of dengue incidence is critical when designing an efficacy trial for a dengue vaccine. In a given city or region, dengue incidence is highly variable from one year to another (variations in geography, season, year-to-year variations in mosquito vector populations in different areas, etc.,) and cannot yet be predicted with sufficient accuracy in many locations being considered for clinical trials. In a dengue vaccine efficacy trial, volunteers are recruited from geographically defined sites. Some of these sites may experience high dengue transmission during the trial duration while others may have limited transmission. Therefore, making a valid assumption regarding the average incidence over time and across sites in order to assess the efficacy of an investigational vaccine is important.

In addition, a critical factor for the success of an efficacy trial is training staff at the various sites to perform study procedures such as febrile illness detection, dengue laboratory diagnosis and data collection in a cohort of subjects.

The proposed study will estimate the incidence of dengue infection and disease across geographically distinct locations in order to validate attack rate assumptions in future efficacy trials. We will enrol individuals from a random sample of households from selected communities of geographically different sites in Brazil and assess incidence of dengue infection and disease, by conducting scheduled serosurveys and an enhanced surveillance of febrile disease.

This study will also prepare potential sites for future clinical trials by setting up the logistics and training staff on site to enrol a cohort of subjects, perform dengue surveillance and other study procedures.

Finally, in line with the overarching strategy of building a strong partnership with the Ministry of Health (MoH), this study will serve as a useful comparison for evaluation of dengue surveillance systems

2. OBJECTIVES

2.1. Primary objective

- To estimate the incidence of laboratory-confirmed symptomatic dengue infection in the study population by year/season.

Refer to Section 8.1.1 for the primary endpoint.

2.2. Secondary objectives

- To estimate the serotype-specific incidence of virologically-confirmed symptomatic dengue infection in the study population overall and by season.
- To estimate the incidence of symptomatic dengue infection (including laboratory-confirmed and probable cases) in the study population by study site, gender, age-group, previous dengue exposure (primary or secondary), overall and by season.
- To estimate the prevalence of previous dengue infection (dengue seroprevalence) in the study population overall and by study site, gender and age-group at enrolment.
- To estimate the incidence of primary inapparent, dengue infection, in the study population overall and by study site, gender age-group and by season.
- To describe symptoms and spectrum of dengue disease in the study population.

Refer to Section 8.1.2 for the secondary endpoints.

2.3. Tertiary objectives (optional) (Amended 16 October 2017)

- To investigate potential risk factors for symptomatic dengue infection.
- To investigate the role of dengue neutralizing antibodies elicited through natural infection in protection against subsequent infection.
- To estimate the degree of underreporting of dengue cases using the passive national notification surveillance.
- *To estimate the incidence of symptomatic Zika virus infection (including laboratory-confirmed and probable cases) in the study population by study site, gender, age-group, previous flavivirus exposure, overall and by season.*
- *To estimate the incidence of symptomatic chikungunya virus infection (including laboratory-confirmed and probable cases) in the study population by study site, gender, age-group, overall, and by season.*
- To describe previous Yellow Fever (YF) antibody profile in selected dengue cases to investigate the role of previous YF immunity on the dengue neutralizing antibody profile following dengue infection.
- To describe the spatial and temporal distribution of dengue cases among cohort participants in the study areas.

- *To describe the spatial and temporal distribution of Zika and chikungunya cases among cohort participants in the study areas.*
- *To describe other infectious aetiologies related to differential diagnosis of dengue (chikungunya and Zika) in subjects with episodes of febrile illness referred to as “suspected dengue case”.*
- *To estimate the seroprevalence of antibodies against Zika and chikungunya virus at selected timepoints.*

Refer to Section 8.1.3 for tertiary endpoints

3. STUDY DESIGN OVERVIEW (AMENDED 16 OCTOBER 2017)

- **Type of design:** Prospective, multicenter, community-based, household-sampling, cohort study in Brazil.
- The study period, initially planned to be one year, has been extended by additional three years (overall four years) to cover three additional dengue seasons (Amendment 2).
- Initial cohort subjects were invited to extend their participation.
- (See [glossary of terms](#) for the definition of initial and expansion cohort subjects).
- In each cohort: replacement subjects may be enrolled in order to compensate for subjects who did not wish to extend their participation for three additional years (for subjects from the initial cohort – Amendment 2), subjects who prematurely terminate participation or subjects who are lost to follow-up.

This will be done to maintain a cohort size of at least 500 subjects per site, in the Initial and Expansion cohorts, at the beginning of each additional study year/season.

In last three months of the of penultimate year of the study, each site will review the number of active subjects and drop-out rate. If the risk of having fewer than the required number of active participants at the end of the study is high, recruitment for participants into the replacement cohort may be performed with sponsor approval. If the risk is high, recruitment into the replacement cohort should begin even if the number of active subjects is 500 or above 500.

(See [glossary of terms](#) for the definition of replacement subjects, subjects lost to follow-up and subjects who prematurely terminate participation).

- Informed consent (and assent, if applicable) will be obtained:
 - From the subject (and parents/LAR of the subjects, if applicable) at the study start for the initial cohort.
 - From the subject (and parents/LAR of the subjects, if applicable) of the initial cohort prior to participation in the additional three years of the study.
 - From the subject (and parents/LAR of the subjects, if applicable) at the study start for the expansion cohort.

[figure not shown]
- From the subject (and parents/LAR of the subjects, if applicable) prior to enrolment in the study for the replacement subjects.
- **Study population:** Subjects six months of age and older at the time of enrolment, who either live in households in study areas with support from the Family Health Physician Program (FHP) or the Larval Index Rapid Assay (LIRA) or with field research experience in the community (preferred) or where a similar system of mapped communities with potential for surveillance exists.
- There will be 2 waves of enrolment for recruiting 3600 subjects:
 - Initial Cohort = about 1800 subjects – up to 6 visits (Amendment 2) – INITIAL sites
 - Expansion Cohort = about 1800 subjects – up to 4 visits – NEW sites
- **Study visits:** The visits will be as follows and further shown in [Figure 1](#):
 - Initial cohort subjects consenting to extend participation for the three additional years will have:
 - three scheduled visits in the first year (Visit 1, Visit 2 and Visit 3) at approximately six months intervals (*+/- 28 days*),
 - and thereafter, one scheduled visit per year preferably during a period of low dengue transmission for the three additional years; i.e., one visit at study Year 2, Year 3 and Year 4 (Visit 4, Visit 5 and Visit 6 respectively).
 - Initial cohort subjects who do not consent to extend participation for three additional years will:
 - have three scheduled visits (Visit 1, Visit 2 and Visit 3) at approximately six months intervals (*+/- 28 days*).
 - conclude their participation in the study at Visit 3 or the last follow up visit if the subject is suspected of having a dengue case on-going at Visit 3.
 - Subjects from the expansion cohort will have only three years of follow-up, with at most 4 scheduled visits.
 - For replacement subjects, the number of scheduled visits will depend on the study year in which they are enrolled. Replacement subjects will not be enrolled until after the third visit of the first study year is concluded for the initial cohort. The number of scheduled visits will range between two and four.

The yearly scheduled visits for the initial and expansion cohorts and replacement subjects will preferably occur during the period of usually low dengue transmission.

In last three months of the penultimate year of the study, each site will review the number of active subjects and drop-out rate. If the risk of having fewer than the required number of active participants at the end of the study is high, recruitment for participants into the replacement cohort may be performed with sponsor approval. If the risk is high, recruitment into the

replacement cohort should begin even if the number of active subjects is 500 or above 500.

Figure 1 Schematic representation of the scheduled visits

V=Visit

The scheduled visits for initial cohort subjects are shown in black.

New enrolments will be done yearly (as needed) till the end of study Year 3.

Enrollment of expansion cohort subjects will start preferably during study Year 2

For replacement subjects, the number of visits will depend on the year enrolled.

- **Type of study:** self-contained
- **Data collection:** Electronic Case Report Form (eCRF)
- **Duration of the study:** Four years for the overall study. For an individual subject, it will range between one and four years.
 - **Epoch 001:** prospective data collection starting at Visit 1, Day 0 and ending at the last subject last visit .

Table 1 Study groups and epochs foreseen in the study

Study Group	Number of subjects*	Age (Minimum)	Epoch
Prospective study cohort	Initial Cohort: 1800 at enrolment (first year) At least 1500 in each subsequent year	6 months and older	Epoch 001
	Expansion Cohort: 1800 at enrolment (first year). At least 1500 in each subsequent year		

*The final number of participants will take into account the active subjects, subjects who prematurely terminate participation and subjects lost to follow up.

3.1. Discussion of study design

3.1.1. Selection of study sites

Selection of study sites

At least six sites covering different regions of the country will be selected for this study. Selection criteria of the sites include support from the Family Health Physician Program (FHP), the Larval Index Rapid Assay (LIRA) or with field research experience in the community. The FHP is a Brazilian government public health strategy that consists of multidisciplinary teams of health care workers that cover geographically defined areas to provide basic/preventive care to community members. The teams include a doctor, a nurse, a nurse auxiliary, and community health care workers who pay regular visits to the household under its responsibility to deliver health promotion activities and facilitate triage and referral into the health unit, among other activities. Community health care workers are local residents who are trained for basic tasks.

LIRA is an alternative vector surveillance strategy that consists of random sampling of a number of dwellings in which surveillance of *Aedes*-positive breeding places is carried out, and has been widely implemented in Brazil (Pontes, 2000).

At least one community of households within each site will be selected.

3.1.2. Rationale for study design

A single cohort study was chosen to estimate the incidence of dengue in the community. Data will be collected from a population of individuals aged 6 months and older for maximum four dengue seasons. Inclusion of individuals of various ages will further allow for a better understanding of disease dynamics, clinical spectrum, and validate attack rates for potential subgroups to be included in future dengue vaccine trials.

This study will use cluster (household) sampling to take into account the correlation that may exist within households. Individuals within a household are expected to have a more similar risk of infection compared to individuals from different households. For example, individuals living in the same household are more likely to share similar risk of being exposed to DENV infected mosquitoes. The sample size has been adjusted to account for this between-cluster variability.

A possible bias *may arise from the* non-response rate. *To reduce the possibility of this potential bias, visits will be scheduled* on weekends or at times *more convenient to the subject*. Where applicable, FHP community health care workers will facilitate communication between study staff and participants.

4. STUDY POPULATION

Subjects six months of age and older at the time of enrolment who live in the selected study sites in Brazil, covering different regions of the country.

4.1. Selection of communities

This study plans to enrol a sample of subjects from randomly selected households from different communities within the selected sites. Community selection is based on the following characteristics:

- preferably areas where the Brazilian FHP or LIRA has been fully implemented or where access to the community is already established by a government program, e.g., registry of families by Secretary of Health, or other institutional program, such as university, in order to allow for random sampling of households;
- safe access by study personnel;
- high population density; and
- low migration rate.

4.2. Selection of households

Households will be randomly selected through LIRA strategy or from a list provided by the FHP or equivalent.

The FHP or LIRA will provide an exhaustive list of households to the study sites and will serve as the liaison between the study personnel and the household, and will not have any other role in this study.

Sites with access to LIRA will use LIRA's specific sampling strategy. LIRA's sampling strategy (preferred strategy) consists of dividing the administrative neighbourhoods of the city into blocks in which each building is enumerated by a unique code number. Within each block a corner is chosen and moving leftward, one in every four houses is systematically selected for vector inspection.

Where LIRA is not implemented but has FHP coverage, a random sample of households will be selected from the FHP database.

Where another type of household registry offers the only access to the community, a random sample will be drawn from the registry database.

Refer to Section 8.2 for a detailed description of the criteria used in the estimation of sample size.

4.3. Overview of the recruitment plan

At least 3600 subjects will be recruited in the study in 2 waves of enrolment. Each wave, initial and expansion cohorts, will enrol about 600 subjects/site in order to maintain at least 500 subjects/site at the beginning of each dengue season.

Subjects will be recruited from randomly selected households originating from pre-selected mapped communities. Preferably the recruitment period will occur outside of the peak dengue transmission season, and will continue until each site has reached its foreseen target. The expected period for recruiting the target sample size is approximately three months. Recruitment of replacement subjects will be done during the low dengue transmission and the recruitment period will depend on the number of subjects that need to be replaced.

Recruitment will be organized by study staff at participating sites according to the appropriate strategy for each site. Community agents or equivalent will serve as the liaison to schedule visits and may accompany study staff during the visits. The study will be explained to the individuals living in the household, and if any individual is interested in study participation, informed consent (and assent when applicable) will be obtained, eligibility criteria will be checked and subjects will be enrolled and interviewed for potential study participation.

If the target household is found empty or all members refuse to participate, the first household to the left will be approached. Those households refusing to participate will be recorded as such. A household refusal will be characterized when all individuals in the household refuse to participate in the study. Individual refusals in a given household will not preclude inclusion of other *individuals living in the households*, and will be recorded as such.

In the subsequent study years/seasons, the cohort size will be maintained at *a minimum of* 500 subjects per site. Since subjects who prematurely terminate participation and/or lost to follow-up will be replaced, the final number of participants across the four study years may exceed 3600 subjects. Yearly, there will be an evaluation of active subjects. If the number of active subjects/site becomes < 500 , there will be enrolment of replacement subjects to maintain a cohort size of at least 500 subjects/site. Enrolment will preferably take place during the low dengue transmission. Recruitment of replacement subjects could occur at the end of study year 1, 2 or 3. The recruitment approach will be the same as for the initial enrolment.

In order to better represent the Brazilian population distribution, subjects enrolled in the expansion cohort should be composed of at least 30% of subjects younger than 18 years old and should not exceed 20 % of adults 50 years or older. Subjects enrolled as replacement subjects for the initial and expansion cohort will be recruited to approach as much as possible a minimal representation of 30% of subjects younger than 18 years old and a maximal representation of 20% for adults 50 years or older.

Household visits may be scheduled to occur during weekends or at convenient times (like evenings) if deemed necessary.

4.4. Inclusion criteria for enrolment (Amended 16 October 2017)

All subjects must satisfy ALL the following criteria at study entry.

- Written, signed or thumb-printed informed consent (and assent when applicable) must be obtained from the subject or subject's parent(s)/LAR(s). If the subject/subject's parent(s)/LAR(s) are illiterate the consent form will be countersigned by a witness.
- Male or female at least 6 months of age at the time of enrolment.
- Subject and/or subject's parent(s)/LAR(s) who the study staff believes can comply with the requirements of the protocol (e.g., willingness to go to the hospital/clinic for visit/s if dengue, *Zika and/or chikungunya* is suspected, able to observe the signs of dengue, *Zika and/or chikungunya* and to understand how to take and report body temperature, etc.).
- Subject who plans, at the time of enrolment, to remain at same residence/study area during their study participation period.

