5.5.3. Procedures at subsequent scheduled visits (2-6, as applicable) (Amended 16 October 2017)

- For initial cohort subjects, Visit 2 will occur approximately 6 months after Visit 1 and Visit 3 approximately 6 months after Visit 2. Initial cohort subjects willing to extend their participation to three additional years will be re-consented at Visit 3 (i.e. at the end of study Year 1).
- For expansion cohort subjects, scheduled visits should ideally be performed at yearly intervals, preferably during periods of usually low dengue transmission. Expansion cohort subjects will have at most 4 scheduled visits, depending on the time of enrolment.
- For replacement subjects enrolled in the subsequent study years, scheduled visits should ideally be performed at yearly intervals, preferably during periods of usually low dengue transmission.
- A blood (serum) sample will be collected for serology.

Note: Indirect DENV IgG assay is repeated in the following scheduled visits (after enrolment) only if the subject was negative for DENV IgG at the previous scheduled visit.

Zika IgG assay is repeated in the following scheduled visits (after enrolment) only if the subject was negative for Zika IgG at the previous scheduled visit.

Chikungunya IgG assay is repeated in the following scheduled visits (after enrolment) only if the subject was negative for chikungunya IgG at the previous scheduled visit.

Even if the tests are not repeated, the volume of the blood sample remains unchanged.

- ***Socio-demographic and household information will be updated in eCRF (for e.g. change of home location).***
- Medical and vaccination histories will be updated in the eCRF.
- The investigator will remind the subjects about the procedures in case of signs and symptoms of dengue, ***Zika and chikungunya.***

- A new diary log will be distributed for continued dengue, *chikungunya and Zika* surveillance if needed, and any completed diary logs will be verified, as applicable. Subjects will be asked to contact the study staff in the event of the occurrence of a symptom that may be associated with suspected dengue, *chikungunya or Zika* (see Section 5.7.1.1, 5.7.2 and 5.7.3 for suspected dengue, *chikungunya or Zika* definition).
- The subject will be instructed to start recording any symptoms, *including rash* and body temperature any time dengue, *chikungunya and/or Zika* is suspected. Refer to Section 5.6.1 for details.
- Any SAEs related to study procedures will be recorded.

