5.7.1.5. Previous dengue infection (Amended 16 October 2017)

A subject will be considered as having previous dengue infection at visit 1 (baseline) if:

- Dengue IgG positive at visit 1 (baseline)
- or
- Laboratory-confirmed symptomatic dengue case detected at visit 1 (baseline)

A subject will be considered as having previous dengue infection at any time after visit 1 (baseline), if:

- *Dengue IgG positive at previous schedule visit(s)*
- or
- *Laboratory-confirmed symptomatic dengue case detected previously at study surveillance*

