1. DOCUMENT HISTORY

Date	Description	Protocol Version
29-OCT-2019	Amendment 1*	Amendment 4: 16 Oct 2017
14-JUN-2019	Final version	Amendment 3: 09 JAN 2015

[figure not shown]
- * In 2017 GSK vaccines has decided to terminate the development of a dengue vaccine. Accordingly none of the tertiary objectives will be evaluated and the analyses additional to those planned in the protocol have been removed from the first statistical analysis plan. In addition in light of the low number of dengue episodes, the large number of positive anti-dengue IgG at visit 1 and the number of dengue cases reported outside the season,
- (1) The analyses of PCR confirmed cases (only 10 cases) and the analyses of secondary dengue infections were removed.
 - (2) The analyses by seroprevalence at each visit were removed,
 - (3) The analyses by season were removed. Only the analyses by calendar year are to be conducted
 - (4) Subjects without seroprevalence status at visit 1 were removed from the ATP cohort because serological status of symptomatic/inapparent dengue infections cannot be assessed properly for such subjects
 - (5) Planned analyses of medical and vaccination history were removed.
 - (6) The statistical method was updated to ignore the household cluster effect and to provide incidence rate with confidence interval in absence of dengue episodes in a calendar year for a study site .

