6.10. Previous dengue infection

A subject will be considered as having previous dengue infection at visit 1(baseline) based on seroprevalence at visit 1, namely if:

- Dengue IgG positive (ie reactive) at visit 1 (baseline) or
- Laboratory-confirmed symptomatic dengue case detected at visit 1 (baseline)

A subject will be considered as having previous dengue infection at any time after visit 1 (baseline), if:

- Dengue IgG positive (ie reactive) at previous schedule visit(s) or
- Laboratory-confirmed symptomatic dengue case detected previously at study surveillance

This status will be considered as unknown for subjects without laboratory result at baseline Visit 1.

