7.1.2. Additional considerations

The number of subjects enrolled into the study will be tabulated by study site and overall on the Total cohort.

The number of subjects enrolled per household will be tabulated by study site and overall on the Total cohort.

The numbers of withdrawn subjects will be tabulated according to the reason for withdrawal by study site and overall on the Total cohort.

The distribution of the subjects in the ATP cohort and reasons for exclusion will be tabulated by study site and overall.

Demographic characteristics (age at Visit 1, age category at visit 1: < 1 year, 1-4 year, 5-8 year, 9-17 year, 18-49 year, >= 50 years, seroprevalence at visit 1 and gender) will be summarized using descriptive statistics by study site and overall on the ATP cohort.

Socio-economic characteristics of the households at Visit 1 (enrolment visit) will be tabulated by study site and overall on the ATP cohort.

The planned analysis of medical and vaccination history was removed.

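### A positive dengue IgG at Visit 1 counts as past infection even in infants from 6 months, where it could be maternal antibody, and no scheduled test revisits it

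*Protocol*

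**What the plan says.** - **Eligibility.** Protocol 4.4: "Male or female at least 6 months of age at the time of enrolment". Section 4.5 has no exclusion or special rule for infants.
- **Status at baseline.** Protocol 5.7.1.5 accepts "Dengue IgG positive at visit 1 (baseline") as sufficient evidence of previous dengue infection. SAP Amendment 1, section 6.10, has the same criterion: "Dengue IgG positive (ie reactive) at visit 1 (baseline) or" a laboratory-confirmed case detected at that visit. Neither has an age condition.
- **Status later.** Protocol 5.7.1.5 carries a positive forward: "Dengue IgG positive at previous schedule visit(s") is enough at any time after Visit 1.
- **Retesting.** Protocol 5.5.3: the indirect IgG assay "is repeated in the following scheduled visits (after enrolment) only if the subject was negative for DENV IgG at the previous scheduled visit". SAP section 7 confirms that from Visit 2 onwards scheduled results exist only for subjects who were negative the time before.
- **Where the status is used.** Protocol 8.5.2 and SAP 7.2.1 divide primary inapparent infections by the number IgG negative at the preceding visit. SAP 6.7 calls a symptomatic case primary only if IgG was absent at the preceding scheduled visit.
- **What the SAP still reports.** Section 3.2 keeps the prevalence of previous infection by age group at enrolment as a secondary objective. Section 7.1.2 lists "age category at visit 1: < 1 year" as a class of its own. Section 7.3.2 still summarises primary diagnosis (yes, no or missing) and inapparent infection.

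Neither document mentions maternal antibody.

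**The concern.** IgG in an infant of 6–11 months may have come from the mother. The SAP's document history refers to "the large number of positive anti-dengue IgG at visit 1", so seropositive mothers are plausible in these communities. One rule for all ages turns such a result into a past infection, and the retest rule makes that permanent. The infant is counted in the prevalence of previous infection. The infant also never enters the seronegative denominator once the maternal antibody has waned, and a later first dengue illness cannot be labelled primary.

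The SAP accepts the underlying principle elsewhere. It removes subjects with no Visit 1 serostatus from the ATP cohort because the type of their infections cannot be judged. An infant whose antibody may be maternal has a similar gap but is handled as known.

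**Working it through.** The plan gives no infant count and no infant seroprevalence, so there is no stated figure to reproduce. The check has two parts: tracing the rules, and a size estimate under assumptions.

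**Tracing one infant.** Enrolled at 7 months, maternal IgG detectable at Visit 1:
1. Classed as previously infected (protocol 5.7.1.5, SAP 6.10).
2. Scheduled IgG is not repeated at Visit 2 or later (protocol 5.5.3).
3. With no later negative, never in the primary inapparent denominator (protocol 8.5.2).
4. A first dengue illness is classed as secondary (protocol 5.7.1.7, SAP 6.8). Acute and convalescent tests at a suspected-case visit do not reset the scheduled serostatus.
5. No planned analysis separates maternal antibody from infection. Neutralisation was an optional tertiary assay, and SAP 7.4 drops the tertiary objectives.
6. Person-time for the primary endpoint runs from enrolment whatever the serostatus (protocol 8.5.2), so confirmed cases and follow-up in this infant still count.

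**Number of infants.** Inputs:
- Five sites opened; Campo Grande never enrolled (SAP 2.1).
- About 600 subjects per site (protocol 4.3); replacements ignored.
- Children were 19% in the first two sites (protocol Appendix C, rationale for Amendment 3), taken as under 18: 2 × 600 = 1200 subjects.
- The 30% target for under-18s was applied at enrolment in Salvador, Natal and Campinas (SAP 2.2.4): 3 × 600 = 1800 subjects.
- Assumption: ages uniform from 6 months to 18 years, so 6–11 months is 0.5/17.5 of the children.

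Infants = 0.5/17.5 × (0.19 × 1200 + 0.30 × 1800) = 0.5/17.5 × 768 ≈ 22.

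**Misclassified.** Assumption: 5–50% carry detectable maternal IgG at Visit 1. Then 22 × 0.05 ≈ 1 to 22 × 0.50 = 11.

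**All-age seroprevalence.** 1/3000 = 0.03 to 11/3000 = 0.37 percentage points upward.

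**Within the under-1 class.** Assumption: 1–5% infected per year, so true prior infection t is between 0.5 × 1% = 0.5% and 1 × 5% = 5%. With maternal share q, the observed proportion is t + (1 − t)q:

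| t | q | Observed | Share of positives that are maternal only |
|---|---|---|---|
| 0.5% | 5% | 5.5% | 91% |
| 5% | 5% | 9.8% | 49% |
| 0.5% | 50% | 50.3% | 99% |
| 5% | 50% | 52.5% | 90% |

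The last column is (1 − t)q divided by the observed proportion.

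**Loss from the primary-infection denominator.** If true all-age seroprevalence is 60–80% (assumed), 3000 × 0.40 = 1200 to 3000 × 0.20 = 600 subjects are truly seronegative. Losing 1 to 11 of them is between 1/1200 = 0.1% and 11/600 = 1.8%.

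**The case against.** The strongest reply is that the key quantity is not in the documents. Nothing there says how long maternal IgG stays detectable by this ELISA, in what share of infants, or how many infants were enrolled. That stands, and it is why the size is given only as a range.

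SAP Amendment 1 also narrows the consequences. Section 7.2.2.1 removes the analyses of secondary infections and of seroprevalence at each visit. Incidence by age is pooled at 17 years or younger. A wrong secondary label therefore reaches only a line in the case summary of 7.3.2. This also stands.

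A reader might infer more than the documents support:
- *That these infants leave the primary endpoint.* They do not. Only the at-risk group for primary infection is affected.
- *That the under-1 figure would mostly measure maternal transfer.* With 5% true infection and 5% maternal carriage, about half the positives are genuine. It could be mostly maternal; that is not shown.
- *That the SAP plans seroprevalence by the under-1 class.* Section 7.1.2 lists age class and Visit 1 serostatus as separate descriptors, and 7.2.2.2 says only that seroprevalence is summarised with demography. The explicit plan by age category is in the superseded June 2019 SAP. The age-group objective in 3.2 remains, without naming classes.
- *That about 30 infants are involved.* That needs the full 3600 subjects and 30% children at every site, and neither held.

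The reply does not remove the rule itself: as written, it assigns an origin to infant IgG that a single test cannot establish.

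**Conclusion.** The point holds as a minor defect in a definition. Protocol 5.7.1.5 and SAP 6.10 count IgG that could be maternal as past infection in subjects under 12 months, and the retest rule fixes that status for the rest of follow-up. It touches a secondary objective (prevalence of previous infection by age group), the primary inapparent denominator and the primary/secondary label. The estimate of about 22 infants rests on 600 per site, uniform ages and no replacements. The estimate of 1 to 11 misclassified rests on the assumed 5–50% maternal carriage. The effect on all-age results is negligible. It matters only if a figure for under 1 year is shown or quoted, because that figure could be several times the true value.

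**What to change.** In SAP 6.10 add a rule for subjects under 12 months at Visit 1:
- Class a positive IgG as *IgG positive, origin undetermined*, not as previous infection.
- Leave these infants out of both numerator and denominator of the previous-infection prevalence, or report them in a separate row.
- Set their primary/secondary status to missing in the section 7.3.2 summary.
- State that they do have a Visit 1 result, so that code 2020 (SAP 5.1) does not remove them from the ATP cohort and hence from the primary incidence.

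The departure from protocol 5.7.1.5 should be described and justified in the study report, as protocol 8.4 requires.

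Optional, where consent allows: test the next stored scheduled serum. Protocol 5.5.3 keeps the blood volume unchanged when the assay is skipped, and 5.8 provides for storage of up to 10 years. A negative returns the infant to the primary-infection at-risk group from that visit. A positive stays undetermined, since it could be persisting maternal antibody, earlier infection or infection since Visit 1. Retesting adds no at-risk interval for Campinas or the Manaus replacements, who have only Visits 1 and 2, and at most one for Natal (SAP section 7).

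Cost: a short SAP paragraph, a slightly smaller evaluable group in the youngest class and, if the option is taken, at most about a dozen assays. Because the study has ended, those assays would be new laboratory work. The relabelling needs none.
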